10.3.3 Evaluation of Best Overall Response

The best overall response is the best response recorded from the start of the treatment until disease progression/recurrence (taking as reference for progressive disease the smallest measurements recorded since the treatment started). The participant's best response assignment will depend on the achievement of both measurement and confirmation criteria.

For Participants with Measurable Disease (i.e., Target Disease)						
Target Lesions	Non-Target Lesions	New Lesions	Overall Response	Best Overall Response for when Confirmation is Required:		
CR	CR	No	CR	> 4 wks confirmation		
CR	Non-CR/Non-PD	No	PR			
CR	Not evaluated	No	PR	≥ 4 wks confirmation		
PR	Non-CR/Non-PD/Not evaluated	No	PR			
SD	Non-CR/Non-PD/Not evaluated	No	SD	Documented at least once > 4 wks from baseline		
PD	Any	Yes or No	PD			
Any	PD*	Yes or No	PD	No prior SD, PR or CR		
Any	Any	Yes	PD			

* In exceptional circumstances, unequivocal progression in non-target lesions may be accepted as disease progression.

Note: Participants with a global deterioration of health status requiring discontinuation of treatment without objective evidence of disease progression at that time should be reported as "symptomatic deterioration". Every effort should be made to document the objective progression even after discontinuation of treatment.

10.3.4 Duration of Response

Duration of overall response: The duration of overall response is measured from the time measurement criteria are met for CR or PR (whichever is first recorded) until the first date that recurrence or PD is objectively documented, taking as reference for PD the smallest measurements recorded since the treatment started.

Duration of overall complete response: The duration of overall CR is measured from the time measurement criteria are first met for CR until the first date that recurrent disease is objectively documented.

Duration of stable disease: Stable disease is measured from the start of the treatment until the criteria for progression are met, taking as reference the smallest measurements recorded since the treatment started.

10.3.5 Progression-Free Survival

Progression-Free Survival (PFS) is defined as the duration of time from start of treatment to time of objective disease progression.

10.3.6 Response Review

Radiology assessments for DF/HCC sites will be provided by the DF/HCC tumormetrics core. Assessment for other participating sites should be performed per local protocols. All complete or partial responses should be confirmed by the DF/HCC tumormetrics core. Please see Appendix I for procedures for submission of materials for DF/HCC tumormetrics review from non-DF/HCC participating institutions.

11. ADVERSE EVENT REPORTING REQUIREMENTS

11.1 Definitions

11.1.1 Adverse Event (AE)

An adverse event (AE) is any undesirable sign, symptom or medical condition or experience that develops or worsens in severity after starting the first dose of study treatment or any procedure specified in the protocol, even if the event is not considered to be related to the study.

Abnormal laboratory values or diagnostic test results constitute adverse events only if they induce clinical signs or symptoms or require treatment or further diagnostic tests.

Please see Section 6.1, "Anticipated Toxicities" for specific information about expected toxicities for both study agents.

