1.3 Secondary Objectives

- To assess the duration of progression-free (PFS) and overall survival (OS) following initiation of therapy with GSK1120212 (trametinib) and GSK2141795
- To determine the nature and degree of toxicity of GSK1120212 (trametinib) and GSK2141795 as assessed by version 4.0 of the NCI Common Terminology Criteria for Adverse Events (CTCAE) in this cohort of patients.
- To describe the mutation and co-mutation rates of genes in the PI3K and RAS-ERK signaling pathways in recurrent cervical cancer using high throughput targeted mutational analysis on participant tumor samples.
- To explore the association of mutational status with clinical benefit from GSK1120212 (trametinib) and GSK2141795.

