Management and Dose Modification Guidelines for Hypo- or Hyperglycemia			
Criteria	Management Guidelines	Study Drug Modification	
(For management purposes, r reporting use NCI-CTCAE version	(For management purposes, refer to mild, moderate and severe intensity criteria; however for eCRF reporting use NCI-CTCAE version 4.0 Grades 1-5)		
Mild Fasting blood glucose > 150mg/dL	Monitor fasting and preprandial glucose.	Continue study drug	
Moderate to Severe Fasting blood glucose <70 mg/dL OR any blood glucose > 250mg/dL	 If a blood glucose >250 mg/dL, monitor for ketoacidosis as clinically indicated. When managing hyperglycemia associated with GSK2141795, be aware that the action of insulin or other antihyperglycemic agents (e.g., sulfonylureas, biguanides, etc.) may be substantially blocked by the study agent. However the action of antihyperglycemic agents would be restored as GSK2141795 is cleared. The patient should be observed closely for rebound hypoglycemia as GSK2141795 is held/or discontinued. Intravenous insulin treatment is recommended. 	Hold GSK2141795 and notify investigator immediately. The investigator should discuss intervention and possible resumption of GSK2141795 with the PI.	

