6.4 Dose Adjustment/Stopping Safety Criteria for Other Clinically Significant Toxicities

Dose modification guidelines are outlined in the table below for clinically significant toxicities, including hematologic toxicities, that are deemed related to study medication(s) but are not addressed above. If a given toxicity is considered by the

investigator to be related to a single investigational drug and not both, then dose modification may occur only with the drug associated with a specific toxicity or event of clinical concern.

Dose Modification Guidelines for GSK1120212 (trametinib) and/or GSK2141795	
Toxicity Grade ^a	Dose Modification of GSK1120212 (trametinib) and/or GSK2141795
Grade 1	Continue at current dose level. Consider supportive care recommendations.
Grade 2	Consider withholding dose until toxicity resolves to Grade 1 or baseline. Upon resolution, then restart at current dose level. Consider supportive care recommendations.
Grade 3	Withhold dose until toxicity resolves to Grade 1 or baseline. Upon resolution, then consider dose reducing by next lower dose level. Consider supportive care recommendations.
Grade 4	Permanently discontinue study medications.

a. Considered related to study drug.

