11.2 Procedures for AE and SAE Recording and Reporting

Participating investigators will assess the occurrence of AEs and SAEs at all participant evaluation time points during the study.

All AEs and SAEs whether reported by the participant, discovered during questioning, directly observed, or detected by physical examination, laboratory test or other means,

will be recorded in the participant's medical record and on the appropriate study-specific case report forms.

The descriptions and grading scales found in the revised NCI Common Terminology Criteria for Adverse Events (CTCAE) version 4 will be utilized for AE reporting. All appropriate treatment areas should have access to a copy of the CTCAE version 4. The CTCAE version 4 can be downloaded from the CTEP website at: http://ctep.cancer.gov/protocolDevelopment/electronic_applications/ctc.htm

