14.1.3 Secondary Objectives

- To assess the duration of progression-free and overall survival following initiation of therapy with GSK1120212 and GSK2141795
- To determine the nature and degree of toxicity of GSK1120212 and GSK2141795 as assessed by version 4 of the NCI Common Terminology Criteria for Adverse Events (CTCAE) in this cohort of patients.
- To describe the mutation and co-mutation rates of genes in the PI3K and RAS-ERK signaling pathways in recurrent cervical cancer using high throughput targeted mutational analysis on participant tumor samples.
- To explore the association of mutational status with clinical benefit from GSK1120212 and GSK2141795.

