14.2 Statistical Analysis

The primary objective of this study is estimation of the best objective response rate (CR + PR) per RECIST 1.1. With the planned accrual of 35 participants to this single-arm trial, there is 91% power to detect an improvement in response rate from 0.07 to 0.22 using a one-sided 0.09-level exact binomial test. Therefore, the null hypothesis will be rejected if 5 or more participants respond to combination therapy with GSK1120212 and GSK2141795. The null hypothesis of 0.07 is based on a weighted average of the observed response rates from the 11 cohorts enrolled to GOG 127 and 227 series.

Secondary objectives include progression-free and overall survival, both of which will be estimated by the Kaplan-Meier method. PFS is defined as the time from registration to the study until documented disease progression or death without progression, whichever occurs first. Participants not experiencing a PFS event will be censored at the last date of documented disease evaluation. Overall survival is defined as the time from study registration to the time of death from any cause, with follow-up censored at the last date

known to be alive. Cox's proportional hazards models will be fitted to explore significant predictors of event-time endpoints.

Toxicity data will be tabulated and compared between any groups of interest using Fisher's exact tests, and will be routinely monitored, analyzed and reviewed by the DF/HCC DSMC.

Molecular correlative analyses will be conducted and all patient outcomes: response, PFS, OS and toxicity will be compared between the PIK3CA and RAS-isoform mutated and WT groups using the statistical methodologies specified above; estimating the proportion of participants harboring mutations in both genes is also of interest, as is comparing their outcomes to those in the remainder of the cohort. These analyses are considered exploratory and will not be adjusted for multiple comparisons.

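### The adverse event definition does not count a dose hold, delay, reduction or discontinuation as making a laboratory abnormality an AE, so the CTCAE toxicity tables may be biased downward

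*Combined protocol and SAP*

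**What the plan says.** Section 11.1.1 states that abnormal laboratory or diagnostic results "constitute adverse events only if they induce clinical signs or symptoms or require treatment or further diagnostic tests". Section 1.3 gives a secondary objective: "To determine the nature and degree of toxicity of GSK1120212 (trametinib) and GSK2141795 as assessed by version 4.0 of the NCI Common Terminology Criteria". Section 14.1.3 repeats it. For the analysis, Section 14.2 says "Toxicity data will be tabulated and compared between any groups of interest" and describes no separate analysis of laboratory grades.

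Section 11.2 has AEs recorded however they come to light, including those "directly observed, or detected by physical examination, laboratory test or other means". The glucose table in Section 6.3.3 uses its own intensity categories for management, then adds "however for eCRF reporting use NCI-CTCAE version 4.0 Grades 1-5", with no condition about symptoms, treatment or tests.

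Several sections act on laboratory values directly. The table in Section 5.1 sets laboratory limits for starting each later cycle. Section 6.3.3 holds GSK2141795 on glucose thresholds. Sections 6.4 and 6.4.2 withhold, discontinue or remove from protocol by toxicity grade, with hematologic toxicity included.

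**The concern.** CTCAE v4 is the stated measuring instrument, and the plan itself grades laboratory abnormalities with it. Such abnormalities are expected here. Section 6.1.5 lists raised AST and ALT, anemia and thrombocytopenia for trametinib. Section 6.1.6 lists hyperglycemia, hypoglycemia and liver enzyme elevation for GSK2141795. The definition nevertheless decides what reaches the AE form, and it leaves out the consequence that matters most for tolerability: whether the value changed the dose.

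If sites apply the sentence as written, a participant could have a cycle delayed, or treatment stopped, for a value that nobody had to record as an AE. Any omission lowers the laboratory toxicity rates. Sites may also differ on whether a repeat count is a further diagnostic test. The committee review in Section 12.2 lists adverse events that have been reported, so it depends on the same definition.

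**Working it through.** No sample size, power or error rate depends on this definition, so there is no figure of the plan to reproduce. The check sets each asymptomatic abnormality against the three triggers in 11.1.1: symptoms, treatment, further tests.

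| Asymptomatic abnormality | Dosing consequence | Treatment or test attached by the plan | Must 11.1.1 record it? |
|---|---|---|---|
| ANC below 1,000/mcL or platelets below 75,000/mcL at a later cycle (5.1.2 and table) | Cycle may not start | None named; recovery has to be shown by a repeat count | Only if a repeat count is a further test |
| Related grade 3 or 4 hematologic toxicity (6.4); unresolved grade 4 (6.4.2) | Grade 3 withheld, grade 4 discontinued; removal from protocol if not improved to grade 1 within 21 days | Supportive care to be considered at grade 3; no test named | As above |
| Fasting glucose below 70 mg/dL (6.3.3) | GSK2141795 held | The ketoacidosis and insulin guidance addresses high glucose; 6.1.2 recommends careful glucose monitoring | Unclear, yet 6.3.3 asks for CTCAE grades |
| Isolated AST elevation | Limit of 2.5 times ULN in the 5.1 table; grade rules in 6.4 | Every stopping and follow-up trigger in 6.3.5 is keyed to ALT | No trigger named |
| Low-grade AST or ALT, or another mild change needing no action | None | None | No |
| ALT at or above 3 times ULN (6.3.5) | Depends on the stopping criterion | Repeat chemistries if also at least 2 times the screening value; serology, CPK and LDH if no malignant liver involvement | Largely yes |
| ALT at or above 3 times ULN with bilirubin at or above 2 times ULN (6.3.5) | Stopped | Classed as an SAE | Yes |
| Hyperglycemia of grade 2 or more (Section 9 footnote) | By the thresholds in 6.3.3 | Daily home glucose monitoring | Yes, on a reasonable reading |

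The first four rows are the gap that involves dosing. The fifth is the low-grade gap. The last three are largely covered.

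For scale only, take the planned maximum of 35 participants (Section 14.3). One missed participant lowers a rate by 1/35 = 2.9 points; three lower it by 3/35 = 8.6 points. These are conversions, not estimates of how many would be missed.

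A second illustration uses AST. Section 2.2.3 reports AST elevation in 22% of 23 phase I patients on the combination, with 9% at grade 3/4. Let c be the share of grade 1-2 elevations that meet 11.1.1. This is an assumption, because the documents give no value. Assume also that all grade 3/4 cases are recorded. Then recorded rate = 0.09 + c × (0.22 − 0.09), and relative undercount = 1 − rate/0.22.

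- c = 1: 22%, or 7.7 of 35; undercount 0%.
- c = 0.75: 18.75%, or 6.6 of 35; undercount 15%.
- c = 0.5: 15.5%, or 5.4 of 35; undercount 30%.
- c = 0.25: 12.25%, or 4.3 of 35; undercount 44%.
- c = 0: 9%, or 3.15 of 35; undercount 59%.

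The illustration has two limits. The phase I rates are themselves recorded AEs, so 22% may not be the true laboratory incidence. And because 6.3.5 is keyed to ALT, the text does not guarantee that every grade 3/4 AST case is captured, so 9% is not a firm floor.

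**The case against.** The strongest reply is that the definition is wider than it first looks. It admits any asymptomatic value that needs treatment or further testing, and the plan attaches tests to the more serious liver and glucose abnormalities. One liver pattern is an SAE with no symptom condition, and glucose has its own CTCAE reporting instruction. Section 11.1.1 also points to Section 6.1, which lists laboratory toxicities as adverse events, and Section 11.4.1 asks for certain grade 4 events to be reported. A count that stops dosing must be repeated before dosing resumes, and a site could fairly call that a further test. Section 14.2 does not expressly confine toxicity data to events meeting 11.1.1. Finally, dose holds follow the value or grade and not AE status, so the dose rules protect patients either way.

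Most of this stands and limits the extent of the problem. It does not close the gap. Section 11.2 records AEs found by laboratory test, but 11.1.1 decides which findings are AEs. The table in Section 11.6 is likewise framed in terms of AEs. Section 11.4.2 sends non-serious AEs to the toxicity case report forms, and the form schedule in 12.1.2 names no laboratory form, so the documents show no other route by which values would reach the toxicity tables. Whether a repeat count qualifies is left to each site.

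A reader might infer three stronger things. The first is that all asymptomatic laboratory abnormalities are excluded and undercounting is certain; the treatment and test triggers contradict that. The second is that grade 3-4 rates are too low throughout; the ALT and hyperglycemia follow-up contradicts that as a general statement. The third is that dose modifications will have no matching AE; the fields of the treatment and AE forms are not shown, so this cannot be known.

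**Conclusion.** The concern holds in a limited form. Dose action is missing from the triggers in 11.1.1. Read literally, the rule allows asymptomatic cytopenias, low fasting glucose and isolated AST elevation to change dosing without having to be recorded as AEs, and it leaves out low-grade values that need no action. The resulting bias in recorded laboratory toxicity can only be downward. Its size cannot be estimated from the documents. It depends on how many abnormalities are asymptomatic and on how sites interpret further diagnostic tests, and neither is given. For low glucose in particular, Section 6.1.2 describes asymptomatic hypoglycemia at 75 mg/day or more of GSK2141795, while this trial starts at 50 mg, so its frequency here is unknown.

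Sections 11.1.1 and 6.3.3 set different conditions for reporting glucose. The primary response analysis, the sample size and the decision rule are unaffected. What is at stake is a stated secondary objective and the completeness of the AE reports used in safety review.

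**What to change.** In Section 11.1.1, add to the list of triggers: 'or lead to a dose hold, reduction, delay or discontinuation of study treatment'. Reconcile 11.1.1 with the CTCAE grade 1-5 eCRF instruction for glucose in 6.3.3, so that sites have one rule.

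Where laboratory values are captured in the database, add to Section 14.2 a table of worst CTCAE v4 grade per participant for hematology, chemistry and glucose, irrespective of AE status. This also covers low-grade values that the added clause would not reach.

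The clause costs one line and more laboratory entries on the AE forms. The table needs no new patient tests, since the Section 9 calendar already schedules them. It may need extra data entry at the sites, because Section 12.1.2 lists no laboratory form and Section 9 lets some cycle 1 tests be done locally. If that burden is too great, the clause and the glucose reconciliation can stand alone.

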11.1.2 Serious Adverse Event (SAE)

A serious adverse event (SAE) is any adverse event, occurring at any dose and regardless of causality that:

- Results in death.
- Is life-threatening. Life-threatening means that the person was at immediate risk of death from the reaction as it occurred, i.e., it does not include a reaction which hypothetically might have caused death had it occurred in a more severe form.
- **Requires or prolongs inpatient hospitalization** (i.e., the event required at least a 24-hour hospitalization or prolonged a hospitalization beyond the expected length of stay). Hospitalization admissions and/or surgical operations scheduled to occur during the study period, but planned prior to study entry are not considered SAEs if the illness or disease existed before the person was enrolled in the trial, provided that it did not deteriorate in an unexpected manner during the trial (e.g., surgery performed earlier than planned).
- **Results in persistent or significant disability/incapacity.** Disability is defined as a substantial disruption of a person's ability to conduct normal life functions.
- Is a congenital anomaly or birth defect.
- Is an important medical event when, based upon appropriate medical judgment, it may jeopardize the participant and require medical or surgical intervention to prevent one of the outcomes listed above. Examples of such medical events include allergic bronchospasm requiring intensive treatment in an emergency room or at home; blood dyscrasias or convulsions that do not result in inpatient hospitalization, or the development of drug dependency or drug abuse.
- Newly diagnosed cancer (not the cancer under treatment).
- Overdose.

Events **not** considered to be serious adverse events are hospitalizations for:

- routine treatment or monitoring of the studied indication, not associated with any deterioration in condition, or for elective procedures
- elective or pre-planned treatment for a pre-existing condition that did not worsen
- emergency outpatient treatment for an event not fulfilling the serious criteria outlined above and not resulting in inpatient admission
- respite care

11.1.3 Expectedness

Adverse events can be 'Expected' or 'Unexpected.'

Expected Adverse Event

Expected adverse events are those that have been previously identified as resulting from administration of the agent. For the purposes of this study, an adverse event is considered expected when it appears in the current adverse event list, the Investigator's Brochure, the package insert or is included in the informed consent document as a potential risk.

Refer to Section 6.1 for a listing of expected adverse events associated with the study agents.

Unexpected Adverse Event

For the purposes of this study, an adverse event is considered unexpected when it varies in nature, intensity or frequency from information provided in the current adverse event list, the Investigator's Brochure, the package insert or when it is not included in the informed consent document as a potential risk.

11.1.4 Attribution

Attribution is the relationship between an adverse event or serious adverse event and the study treatment. Attribution will be assigned as follows:

- Definite The AE is clearly related to the study treatment.
- Probable The AE is likely related to the study treatment.
- Possible The AE may be related to the study treatment.
- Unlikely The AE is doubtfully related to the study treatment.
- Unrelated The AE is clearly NOT related to the study treatment.

11.2 Procedures for AE and SAE Recording and Reporting

Participating investigators will assess the occurrence of AEs and SAEs at all participant evaluation time points during the study.

All AEs and SAEs whether reported by the participant, discovered during questioning, directly observed, or detected by physical examination, laboratory test or other means,

will be recorded in the participant's medical record and on the appropriate study-specific case report forms.

The descriptions and grading scales found in the revised NCI Common Terminology Criteria for Adverse Events (CTCAE) version 4 will be utilized for AE reporting. All appropriate treatment areas should have access to a copy of the CTCAE version 4. The CTCAE version 4 can be downloaded from the CTEP website at: http://ctep.cancer.gov/protocolDevelopment/electronic_applications/ctc.htm

